3.1 Overall Design

for three months.

The proposed study is a randomized clinical trial comparing BTA to placebo injections into the masseter and temporalis muscles in management of myofascial pain disorder. The hypothesis is that injections of BTA reduces the intensity of myofascial pain more than placebo. Currently, in the literature, there is no evidence for the best non-surgical treatment modality for treatment of myofascial pain disorder of the muscles of mastication. Many different approaches have been described such as oral appliances, medications (NSAIDS and muscle relaxants), physiotherapy, acupuncture, trigger point injections, and botulinum injections. To date, the literature concerning trigger point injections and botulinum injections for treatment of myofascial pain disorders of the muscles of mastication is limited. Currently, injection of BTA is not FDA approved for myofascial pain disorder of the masseters and temporalis muscles.

Eligible participants in the clinical trial will be male and female adults ages 18 – 65 identified as having a myofascial pain diagnosis according to the research diagnostic criteria. All subjects will have myofascial pain disorder. Healthy controls will not be involved in the study. The study design will be a double-blind placebo controlled clinical trial. The participants will receive either a solution of placebo (total 4cc unpreserved 0.9% sodium chloride) injected into the masseters and temporalis muscles or a solution of botulinum toxin A (total of 100 units reconstituted with 4cc unpreserved 0.9% sodium chloride). Both treatment groups are considered investigative. The patients will be stratified into gender groups. The participants will be monitored

The primary outcome measure will be pain measured on a visual analog scale prior to treatment and at one, two and three months post-treatment. Secondary outcome measures performed at the same intervals will be quality of life (short form 36), maximum interincisal opening, and functional status via the jaw functional limitation scale. The only study procedures are the injection of botulinum toxin or placebo and the use of visual analog scale, measurement of maximum incisal opening and the use of visual analog scale and questionnaires.

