4.2 Inclusion Criteria

- 1. 18 65 years of age
- 2. Able to give informed consent
- 3. Myofascial pain of masticatory muscles as defined according to the RDC/TMD criteria
- 4. Baseline pain measured by the subject ≥ 3.5/10 on visual analog scale

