12.1 Study Design/Endpoints

Based on the preliminary data and the sample size calculations estimating a difference in mean prepost VAS change between groups of 1 point or greater (on a scale of 1-10), we plan to enroll a total of 110 subjects between the two study sites. Estimated 55 subjects will be enrolled at Weill-Cornell Medical Center/ New York Presbyterian Hospital and 55 subjects will be enrolled at the University of Illinois at Chicago. With 55 patients in the botulinum toxin A injection group and 55 patients in the placebo group (N=110), the study will have more than 90% power to detect a difference in mean in pre-post change between groups of 1.0 point or greater on VAS, using a two-sided t-test and assuming a standard deviation of 1.5 for the mean difference. This calculation allows for 10% attrition rate.

An intent-to-treat design will be followed and all subjects will have scheduled outcome evaluations until the end of the study, death of the subject, or subject refusal. Subjects will be withdrawn from their randomly assigned treatment for considerations of subject safety only. Descriptive statistics including mean, standard deviation, median, range, frequency, and percent will be calculated for the entire cohort as well as by the study arm (botulinum toxin A and unpreserved 0.9% sodium chloride) to assess the results of randomization and identify potential confounders.

The primary analyses of the data will be performed according to subjects' original treatment assignment (i.e., intention-to-treat analyses) and the inclusion of all data from all subjects randomized in the final analysis. To assess the primary endpoint of improvement of pain on a visual analog scale (VAS) between pre-op, 1, 2, and 3 months post-op, a repeated measure of analysis of variance will be performed with one between subject factor (botulinum toxin A versus placebo) and one within subject factor (time). This analysis will also be used for the secondary endpoints: function (MIO/jaw limitation scale) and quality of life (SF12). In the event of significant loss to follow-up, we will explore the use of a linear mixed model to assess the independent effect of the study group on VAS over the study visits. The paired t-test, or the signed-rank test as appropriate, will be used to assess change in pain, function, and QOL between pairs of relevant time points for both study arms.

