To assess the difference in proportion of adverse events between the botulinum toxin A and placebo groups, either the chi-square or Fisher's exact test will be used, as appropriate. All p-values will be two-sided with statistical significance evaluated at the 0.05 alpha level. Ninety-five percent confidence intervals (95% CI) will be calculated to assess the precision of the obtained estimates.

All analyses will be performed in SAS Version 9.4 (SAS Institute Inc., Cary, NC). Note: This section was drafted in conjunction with [name] and [name] in the Division of Biostatistics and Epidemiology, Department of Healthcare Policy and Research. They will be aiding in protocol design and development, data management, study implementation, study monitoring, and data analysis and reporting.

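### Section 12.1 adds within-arm paired tests, judged at 0.05 and not labelled descriptive; they cannot test Botox against placebo, and no between-arm contrast by visit is specified.

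*Combined protocol and SAP*

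**What the plan says.** Section 3.1 states a comparative aim: "The hypothesis is that injections of BTA reduces the intensity of myofascial pain more than placebo".

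Sections 12.1 and 12.4.1 assign the primary endpoint to a repeated-measures ANOVA with arm as the between-subject factor and time as the within-subject factor. Sections 12.1 and 12.4.2 use the same analysis for function and quality of life. Neither says whether the arm, time or arm-by-time term decides the hypothesis, and no between-arm contrast at a given visit is named.

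The same paragraph of Section 12.1 then adds the paired t-test, or the signed-rank test as appropriate, which "will be used to assess change in pain, function, and QOL between pairs of relevant time points for both study arms". The relevant pairs are not listed and the tests are not called descriptive or supportive. Later in Section 12.1: "All p-values will be two-sided with statistical significance evaluated at the 0.05 alpha level". No multiplicity rule is given.

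On entry, Section 4.2 requires "Baseline pain measured by the subject" to be at least 3.5/10 on the VAS.

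**The concern.** A paired test within one arm compares that arm with its own past. Any improvement that the two arms share, such as placebo response, natural fluctuation or regression to the mean after selection on the outcome, counts in full as change. The between-arm comparison removes it.

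An undeclared set of within-arm p-values at 0.05 therefore invites a familiar misreading: a significant fall on Botox and a non-significant fall on placebo, reported as if that were a treatment effect. The plan does not say that these tests are not evidence of efficacy. They are also its only stated visit-to-visit comparisons, so a reader who wants to know what happened at month 1 or month 3 will be drawn to them.

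**Working it through.** **Inputs from the documents (Section 12.1).** 55 per arm; two-sided alpha 0.05; between-arm difference 1.0 point; SD 1.5, read as the SD of the pre-post change; 10% attrition, so 55 × 0.9 = 49.5, taken as 49 per arm. Four time points (baseline, months 1, 2 and 3).

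**Inputs assumed.** The shared improvement d, and the population mean, SD and visit-to-visit correlation of VAS. The documents give none of these.

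**1. The plan's own figure.** The plan says "the study will have more than 90% power" for a "difference in mean in pre-post change between groups of 1.0 point or greater on VAS". With a two-sample t-test, the noncentrality is 1.0 / (1.5 × √(2/n)). Power is 93.4% at n = 55 and 90.4% at n = 49. The stated power reproduces.

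**2. Smallest significant within-arm fall.** The standard error at n = 49 is 1.5/√49 = 0.214 and the critical t on 48 df is 2.011, so 2.011 × 0.214 = 0.43 points. That is under half of the 1.0-point difference the trial is sized for.

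**3. Chance of within-arm significance with no drug effect.** This is the noncentral t on 48 df with noncentrality d / 0.214. The chance p applies to each arm. The chance that Botox is significant and placebo is not is p(1 − p), because the arms are independent.

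| Shared improvement d (SD 1.5) | Noncentrality | p, one arm | Botox only, p(1 − p) |
|---|---|---|---|
| 0.3 | 1.40 | 28% | 20% |
| 0.5 | 2.33 | 63% | 23% |
| 0.75 | 3.50 | 93% | 7% |
| 1.0 | 4.67 | 99.5% | 0.5% |

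Between 0.3 and 0.5, p passes through 50%, where p(1 − p) reaches its maximum of 25%. Hence the range 20-25%. A valid between-arm test keeps its two-sided 5% error rate at every d.

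The results depend on the SD. At SD 2.5, p is 13%, 28% and 78% for d = 0.3, 0.5 and 1.0.

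**4. Regression to the mean from the 3.5 entry rule alone.** For a normal VAS with mean μ, SD s and visit correlation ρ, selected at 3.5 or above, the expected fall is (1 − ρ) × s × λ. Here λ is the standard normal density at a = (3.5 − μ)/s divided by the upper-tail probability at a.

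- Largest case in the assumed range (μ = 5, s = 2, ρ = 0.5): a = −0.75, λ = 0.301/0.773 = 0.389, fall = 0.5 × 2 × 0.389 = 0.39.
- Smallest case (μ = 5.5, s = 1.5, ρ = 0.7): a = −1.33, λ = 0.164/0.909 = 0.18, fall = 0.3 × 1.5 × 0.18 = 0.08.

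Falls of 0.08 to 0.39 are significant within an arm about 7% to 43% of the time at SD 1.5 and n = 49. With the change SD implied by the same inputs the range is about 8% to 29%. A wider assumed range (μ 4 to 6, s 2 to 2.5, ρ 0.4 to 0.7) gives falls of about 0.1 to 1.0 and significance about 9% to 80% of the time.

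**5. Number of tests.** Outcomes: VAS, maximum interincisal opening, jaw scale and one SF-36 score, so 4. Against baseline only: 3 pairs × 4 × 2 arms = 24. All pairs: 6 × 4 × 2 = 48. The plan does not say which applies, or whether a single SF-36 score is meant.

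**The case against.** The strongest defence is that the hypothesis has its own analysis. The ANOVA with arm as a factor, by intention to treat, is declared for the primary and secondary endpoints. The paired tests come last and are nowhere called primary. Section 1.2.1 speaks of pain before treatment and at each visit in both groups, so describing change within each arm fits a stated objective. Section 12.1 already plans 95% CIs. All of this stands. A reader might infer that the efficacy claim rests on the paired tests, or that randomization is given up; the documents do not support either.

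Three other strong readings also fail.

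- **That every pair of visits is tested.** The text refers only to relevant pairs. The defect is that they are undefined; 48 is an upper bound.
- **That regression to the mean alone will often produce significance.** On the narrower assumptions the chance is below one half throughout. The entry rule acts directly on baseline-to-follow-up VAS pairs. It acts on the other outcomes only through their correlation with VAS, and hardly on pairs of follow-up visits. It also depends on whether the eligibility and baseline scores are one reading, which is unclear: Section 6.1.1 puts the eligibility checklist and the randomization order at the pre-study visit, Section 1.1 lists the checklist at Day 0, and Table 1 schedules no VAS before the treatment visit. With two readings, part of the fall would precede baseline.
- **That a larger shared response makes the misleading pattern more common.** At SD 1.5 it makes both arms significant, and the Botox-only pattern nearly disappears.

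What the defence does not answer is that the tests are planned, unlabelled and judged at 0.05, cannot address the comparative hypothesis, and fill a gap where visit-specific between-arm estimates should stand.

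**Conclusion.** The point holds as a weakness in a supplementary analysis. The within-arm tests cannot answer the question in Section 3.1, and at about 49 per arm they become significant after modest improvement that owes nothing to the drug. The Botox-only pattern is a real hazard, at 20-25% of trials, if the shared improvement is near 0.3-0.5 points, and a small one at 0.75 or more. These figures rest on SD 1.5 for the change, 49 evaluable per arm and an assumed shared improvement. The primary between-arm analysis and the stated power are unaffected. This is a cheap improvement that the plan should make, and it does not threaten the trial's validity.

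**What to change.** In Section 12.1, replace the sentence on paired and signed-rank tests. Report instead the between-arm differences in change from baseline at months 1, 2 and 3, with 95% CIs, estimated from the primary model. Show within-arm changes descriptively (mean, SD, 95% CI), without p-values, and state that they are not evidence of efficacy.

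If the sponsor prefers to keep the paired tests, the minimum is to list the pairs and label the tests descriptive.

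The cost is one amended sentence and the loss of within-arm p-values. No extra data, visits or participants are needed.

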	analog scale prior to treatment and at one, two and three months post-			
	treatment in both the Botox and placebo groups.			
Secondary Objectives:	The secondary objectives will be to compare the quality of life (SF-36),			
	maximum interincisal opening, and functional status via the jaw			
	functional limitation scale in both the Botox and placebo groups.			
Exploratory Objectives:	None			
Endpoints:	The primary endpoint is improvement of pain on a visual analog scale			
	(VAS) between pre-op, 1, 2, and 3 months post-op. The secondary			
	endpoints are function (MIO/jaw limitation scale) and quality of life			
	(SF36)			

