12.4 Analysis of Endpoints

12.4.1 Analysis of Primary Endpoints

To assess the primary endpoint of improvement of pain on a visual analog scale (VAS) between pre-op, 1, 2, and 3 months post-op, a repeated measure of analysis of variance will be performed with one between subject factor (botulinum toxin A versus placebo) and one within subject factor (time). In the event of significant loss to follow-up, we will explore the use of a linear mixed model to assess the independent effect of the study group on VAS over the study visits.

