12.4.2 Analysis of Secondary Endpoints

The same analysis as that of the primary endpoints will also be used for the secondary endpoints: function (MIO/jaw limitation scale) and quality of life (SF36).

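### Secondary endpoints are all judged at 0.05 with no gate, order, adjustment or descriptive label, and the quality-of-life score is not named, so the error rate for secondary claims is above the stated level

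*Combined protocol and SAP*

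**What the plan says.** - **Significance rule.** Section 12.1 states: "All p-values will be two-sided with statistical significance evaluated at the 0.05 alpha level". It makes no distinction between primary and secondary tests. The same section also promises 95% confidence intervals.
- **Secondary endpoints.** Under section 12.4.2 the primary analysis "will also be used for the secondary endpoints: function (MIO/jaw limitation scale) and quality of life (SF36"). The synopsis pairs the two function measures in the same way: "endpoints are function (MIO/jaw limitation scale) and quality of life". No rule says whether one or both must succeed.
- **Quality-of-life instrument.** The synopsis objectives read "The secondary objectives will be to compare the quality of life (SF-36"), and section 3.1 agrees. Section 12.1 differs: "This analysis will also be used for the secondary endpoints: function (MIO/jaw limitation scale) and quality of life (SF12"). No section names a scale or summary score for either version.
- **Model.** Section 12.4.1 specifies "one between subject factor (botulinum toxin A versus placebo) and one within subject factor (time"). It does not say whether the group effect or the group-by-time interaction decides.
- **Further tests.** Section 12.1 adds a paired t-test or signed-rank test that "will be used to assess change in pain, function, and QOL between pairs of relevant time points for both study arms". The pairs are not listed.
- **What is absent.** No section gives a gate on VAS, a testing order, a multiplicity adjustment or a statement that secondary results are descriptive. The synopsis lists no exploratory objectives.

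**The concern.** Under the rule as written, each secondary p-value below 0.05 counts as statistically significant, whatever happens on VAS. Function can succeed on either of two measures. The number of quality-of-life tests is open because no score is fixed. If pain did not separate the arms, a reader of the results could still be shown a significant functional or quality-of-life finding, and the stated 0.05 would not be the error rate for a finding picked from that set. This matters because section 2.4.2 presents better jaw function and quality of life as possible benefits of taking part, and section 3.1 says the use is not FDA approved.

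**Working it through.** **The plan's own figure.** The documents give no family-wise error rate for the secondaries. The only related figure is primary power above 90% (section 12.1: 55 per arm, difference 1.0, SD 1.5, two-sided 0.05, 10% attrition).

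- 55 per arm: SE = 1.5 × √(2/55) = 0.286; 1.0/0.286 − 1.960 = 1.536; power 93.8% (93.4% by the exact t).
- 49.5 per arm after attrition: SE = 0.3015; 3.317 − 1.960 = 1.357; power 91.3% (90.7% by the exact t).

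The stated power reproduces. It concerns VAS alone, so nothing below changes it.

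**Inputs for the secondary family.**

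- Level per test: 0.05 two-sided (section 12.1), which is 0.025 in the direction of benefit.
- Named instruments: three (MIO, jaw limitation scale, SF-36), with one between-group test each.
- Correlation between test statistics: not in the documents; assumed 0, 0.5 and 0.7, equal for all pairs.
- What-if family of 12: MIO, jaw scale and 10 SF-36 scores (8 scales plus 2 summaries). This count is an assumption.

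**Formulas.** With independent tests and an inert drug:

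- any p < 0.05: 1 − 0.95^k
- at least one in favour of the toxin: 1 − 0.975^k

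For k = 3: 1 − 0.95³ = 0.143 and 1 − 0.975³ = 0.073. For k = 12: 1 − 0.95¹² = 0.460 and 1 − 0.975¹² = 0.262. The correlated cases use equicorrelated normal test statistics.

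| Tests | Correlation | Any p < 0.05 | Benefit direction only |
|---|---|---|---|
| 3 (named) | 0 | 14.3% | 7.3% |
| 3 (named) | 0.5 | 12.5% | 6.3% |
| 3 (named) | 0.7 | 10.9% | 5.5% |
| 12 (what-if) | 0 | 46.0% | 26.2% |
| 12 (what-if) | 0.5 | 31.9% | 16.0% |
| 12 (what-if) | 0.7 | 23.2% | 11.6% |

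The reference values for a single test are 5% and 2.5%.

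**Effect of the unnamed deciding term.** Suppose a significant group effect or a significant interaction could each count. A null simulation of the repeated-measures ANOVA (55 per arm, four visits, assumed within-subject correlation 0.5, 3,000 runs) then gives about 27% for three independent endpoints and about 24% at an endpoint correlation of 0.5, in any direction.

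**Within-arm paired tests.** These are left out of the counts. They test change over time inside an arm, not toxin against placebo.

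**After the fix.** Holm's first step for three tests is 0.05/3 = 0.0167. Three independent tests at that level give 1 − (1 − 0.0167)³ = 4.9%.

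**The case against.** The plan has one primary endpoint, VAS pain, and the hypothesis in section 3.1 is about pain intensity only. No section says that a secondary p-value will support a benefit claim if VAS fails. A level per test is conventional and does not promise family-wise control. Unadjusted secondaries read as supportive are common in a two-site trial of 110 subjects, and the promised confidence intervals already supply part of the remedy. This limits the importance of the point but does not remove it: the plan never says that the secondaries are supportive, and its only rule calls each of them significant at 0.05.

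Three stronger readings are tempting, and the documents do not support them.

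- **That a chance secondary benefit is likely.** None of the figures in the table reaches 50%. Passing 50% takes 14 independent two-sided tests, or 28 counting benefit only. Allowing either ANOVA effect to count gets there with about ten endpoints (64% independent, 51% at correlation 0.5), but only in any direction and with assumed scores. The two-sided figures also include results that favour placebo, so they are about twice the risk of a false benefit claim.
- **That the plan tests a multi-scale SF-36.** No scale or summary is named. What the text shows is an undefined score, so the 12-test figures are a what-if only.
- **That the trial's main conclusion is compromised.** Testing secondaries does not alter the type I error of the VAS comparison.

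**Conclusion.** The point holds in a limited form. A flat 0.05 rule covers secondary endpoints that have no gate, order, adjustment or descriptive label, and one of them has no defined score. With the three named instruments, one between-group test each and correlations from 0 to 0.7, the chance of a false positive is about 11–14%, of which about 5.5–7% would look like benefit. With 12 scores, under the assumption about the SF-36, the ranges are about 23–46% and 12–26%. The correlations are assumed throughout. The SF-12/SF-36 conflict and the unnamed deciding effect are gaps in their own right, and no multiplicity procedure can be applied until both are settled. This should be corrected before unblinding, but it does not threaten the primary analysis.

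**What to change.** 1. Reconcile the SF-12 in section 12.1 with the SF-36 elsewhere. In section 12.4.2, name one score per instrument: MIO, the jaw limitation total and one quality-of-life summary score.
2. Name the single between-group effect on which each endpoint, including VAS, is judged.
3. Limit the 0.05 sentence in section 12.1 to the primary VAS contrast and this secondary family. Test the family only if VAS is significant, using Holm at 0.05 or a fixed order.
4. Report all other quality-of-life scales, single-visit results and within-arm paired comparisons as estimates with 95% confidence intervals, without significance claims.

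An equally acceptable and simpler alternative to the gated family in item 3 is to declare the secondaries supportive, report estimates with 95% confidence intervals and make no significance claim on them.

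The cost is plan wording before unblinding. The gated option makes secondary claims harder (0.0167 at the first Holm step, and none if VAS fails). The alternative gives up secondary significance claims altogether. Sample size and primary power do not change under either.

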12.2 Sample Size/Accrual Rate

We plan to enroll 110 subjects in 18 months. About 55 subjects will be enrolled at Weill Cornell Medicine and the remaining 55 will be enrolled at the University of Illinois at Chicago.

12.3 Stratification Factors

Not applicable

